1.1.1.1 Berberine and Ursodeoxycholic Acid

Berberine is an isoquinoline alkaloid found in many different plants, with a long history of use in traditional Chinese medicine (Caliceti et al., 2016, Kumar et al., 2015). Berberine chloride (BBR·Cl) is an approved antiseptic drug in China, Japan, and Taiwan. In the United States (US) and Australia, BBR is widely used in various dietary supplements for a number of advertised health benefits and is grandfathered under the

Dietary Supplement Health and Education Act (DSHEA) in the US (Council for Responsible Nutrition 1998). The reported multi-spectrum activity of BBR, including effects on glucose and lipid metabolism, hepatic steatosis, oxidative stress, inflammation, and fibrosis suggests that BBR has the potential to treat NAFLD/NASH. Furthermore, clinical studies of BBR for the treatment of T2DM, hyperlipidemia, hypertension, and NAFLD have yielded favorable results (Cicero and Ertek 2009, Lan et al., 2015).

Ursodeoxycholic acid is a secondary bile acid produced by intestinal bacteria as a metabolic by-product, which is approved by the US Food and Drug Administration (FDA) for the non-surgical treatment of cholesterol gallstone dissolution (Actigall®, NDA 019594) and the treatment of primary biliary cirrhosis (PBC) (URSO 250® and URSO Forte®, NDA 020675). Similar to BBR, UDCA activity is reported to include anti-oxidative stress, anti-inflammatory, anti-apoptotic, and anti-fibrotic effects, as well as improvement in liver injury caused by microbial dysbiosis. In the clinical setting, favorable results were reported for UDCA combination therapy compared to UDCA monotherapy in the treatment of NASH (Xiang et al., 2013).

Based on the pharmacological properties and clinical evaluations of BBR and UDCA relative to NASH and conditions that are most commonly attributed to its development, BBR and UDCA may present as good "partners" for effectively treating this advanced liver disease. More information about the activity, safety, and efficacy of BBR and UDCA can be found in the HTD1801 Investigator's Brochure.

1.1.1.2 HTD1801

HTD1801 is expected to demonstrate a multi-functional pharmacologic profile reflecting the individual actions of its active components, BBR and UDCA. These agents target multiple aberrant pathways that may contribute to the pathogenesis of NASH. The beneficial effects of HTD1801 in patients with NASH are expected to include, but may not be limited to:

- Improved insulin resistance and regulation of lipid and glucose metabolism;
- Reduction of fat deposition in the liver;
- Restoration of the intestinal barrier function;

- Anti-inflammatory, anti-oxidative, and anti-apoptotic effects;
- Anti-fibrotic effects.

Given the unique pharmacologic profiles of BBR and UDCA, both additive and synergistic effects are expected to occur when the 2 products are administered together as HTD1801. More information about the activity, safety, and efficacy of HTD1801 can be found in the HTD1801 Investigator's Brochure.

1.1.2 Nonclinical Studies

The pharmacology of HTD1801 was evaluated *in vivo* in rodent and primate models of hyperlipidemia/NAFLD:

- HTD1801 was evaluated in a pilot study of high-fat diet-induced Golden Syrian hamsters. After 8 weeks, hamsters administered HTD1801 100 mg/kg or a physical mixture of BBR·Cl and UDCA 100 mg/kg (molar ratio of 1:1) had decreased serum levels of total cholesterol (TC), triglycerides, and malondialdehyde compared to those of a model (untreated) control group; however, the effects were enhanced with HTD1801 compared to the physical mixture of BBR·Cl and UDCA. Hamsters treated with the physical mixture of BBR·Cl and UDCA also exhibited greater decreases in body weight and more serious adverse effects than the group treated with HTD1801.
- HTD1801 was further evaluated in a high-fat diet-induced Golden Syrian hamster model of hyperlipidemia/NAFLD. At doses of 50 mg/kg or 200 mg/kg administered intragastrically for 7 weeks, HTD1801 significantly reduced serum levels of TC, triglyceride, and low-density lipoprotein cholesterol (LDL-c), the ratio of TC/high-density lipoprotein cholesterol (HDL-c), and the atherosclerotic index value, as well as the risk of atherosclerosis, in a dose-dependent manner. Hepatic lipidosis and body lipidosis also were significantly reduced, while hepatic inflammation was ameliorated.
- HTD1801 was evaluated in male Rhesus monkeys with naturally-occurring NAFLD. Study results indicated a dose-dependent reduction of liver steatosis. At 30 mg/kg (equivalent to a clinical proposed dose of 1,050 mg/70 kg person/day), HTD1801 significantly reduced liver steatosis, while at 15 mg/kg (equivalent to a clinical proposed dose of 525 mg/70 kg person/day), a decreasing trend in

steatosis was observed after 69 days of administration. Significant lowering of LDL-c, aspartate aminotransferase (AST), and alanine aminotransferase (ALT) levels was noted, while a treatment-related decreasing trend was observed for TC, apolipoprotein B, and blood glucose levels.

The nonclinical toxicity profiles of both BBR and UDCA have been extensively documented. A full International Conference on Harmonisation (ICH) M3 battery of nonclinical studies of UDCA was submitted in support of NDA 020675. The toxicity profile of BBR was assessed in a battery of nonclinical studies conducted and/or reviewed by the National Toxicology Program. These studies include single-dose oral studies in mice and rats, *in vitro* and *in vivo* genotoxicity studies, and reproductive and developmental toxicity studies in mice and rats (National Toxicology Program 2002, 2003c, a, b, 2010).

The pharmacokinetic (PK) and toxicity profiles of HTD1801 have been evaluated in both rats and dogs. Toxicology studies of up to 2 weeks in rats (non-GLP) and up to 13 weeks in dogs (GLP) have been conducted. Combined administration of BBR and UDCA as HTD1801 yielded PK and toxicity profiles similar to those of the individual components UDCA and BBR. In addition, a 13-week GLP dog study provided data to qualify the toxicity profile of BBR in non-rodents and the safety of the combination of BBR and UDCA when administered as HTD1801.

Available nonclinical study data for HTD1801, together with cumulative nonclinical study data and clinical experience for BBR and UDCA individually, support the safety and tolerability of HTD1801 for this POC study. More information about the nonclinical evaluation of HTD1801 can be found in the HTD1801 Investigator's Brochure.

1.2 STUDY RATIONALE

1.2.1 Rationale for Study Design

This 18-week randomized, double-blind, parallel-group, POC, dose-ranging study will compare multiple doses of HTD1801 to placebo. A randomized, double-blind design will enhance study rigor and quality relative to assessment of the pre-specified endpoints (see Section 3.4). In the absence of approved or recognized therapeutics for NASH, a placebo control group will be utilized, as has been reported for several prior

randomized, placebo-controlled assessments of various pharmacologic agents (Loomba et al., 2008).

Since accumulation of hepatic fat is considered the "first hit" in the pathogenesis of NASH (Adams and Angulo 2006), change in LFC by magnetic resonance imaging-estimated proton density fat fraction (MRI-PDFF) is an appropriate primary endpoint and is consistent with that used in recent Phase 2 POC studies in NASH (Harrison et al., 2018, Madrigal Pharmaceuticals 2018).

1.2.2 Rationale for Dose and Duration

Ursodeoxycholic acid is approved by the US FDA at a dose of 13-15 mg/kg/day (URSO 250® and URSO FORTE®), or approximately 1 g/day for a 70 kg individual. Berberine is widely used in dietary supplements in the US at a recommended dose of 17-33 mg/kg/day, or approximately 1-2 g/day for a 70 kg individual. Furthermore, New Tantose A®, an over-the-counter combination including BBR (adult dose of 0.300 g/day) and UDCA (0.030 g/day), has been approved in Japan for acute diarrheal illness (New Tantose A®), while the therapeutic dosage in most of BBR's clinical experience is around 0.4-2.7 g/day orally for exposures up to 181 days (Cicero and Ertek 2009, Lan et al., 2015). As shown in Table 3, the UDCA and BBR content of HTD1801 are comparable to doses associated with clinical safety.

Table 3. Comparison of HTD1801 Clinical Dose with FDA Approved UDCA Dose and Clinical BBR Dose

| Compound | FDA Approved Clinical Dose (UDCA) / Dose Used in Clinical Experience (BBR) | HTD1801 Clinical Dose (29 mg/kg/day; 2,000 mg/day) ^{a,d} |
|-------------------|--|--|
| UDCA ^a | 13-15 mg/kg/day (910-1,050 mg/day) ^b | 15 mg/kg/day (1,078 mg/day) |
| BBR ^a | 6-38 mg/kg/day (400-2,700 mg/day) ^c | 15 mg/kg/day (1,022 mg/day) |

^a mg/kg doses calculated assuming a 70 kg adult.

Furthermore, data from a first-in-human, single ascending dose study of HTD1801 in healthy subjects (Protocol HTD1801.PCT002) demonstrated dose proportionality for

^b Safety at doses up to 25 mg/kg/day is supported by the published literature for PBC patients (Angulo et al., 1999).

^c Therapeutic dosage in most of BBR's clinical experience (Cicero and Ertek 2009, Lan et al., 2015).

d HTD1801 dose of 2,000 mg/day is equivalent to 1,022 mg/day BBR and 1,078 mg/day UDCA.

UDCA and BBR exposure parameters at orally administered HTD1801 doses of 0.5-4.0 g/day. Single doses of HTD1801 were also safe and well tolerated.

Lastly, recent Phase 2 POC studies in NASH (Harrison et al., 2018, Madrigal Pharmaceuticals 2018) show clinically meaningful absolute and relative reductions in LFC assessed by MRI-PDFF over 12-week treatment periods. An 18-week HTD1801 treatment period is therefore adequate to assess the study's primary endpoint and to maximize collection of exposure and safety related data.

2.0 OBJECTIVES

The primary objective of this study is to evaluate the effects of HTD1801 on LFC in adults with NASH and T2DM.

The secondary objectives of this study are to evaluate:

- 1. The effects of HTD1801 on hemoglobin A1c (HbA1c) and glucose metabolism;
- 2. The effects of HTD1801 on lipid profile;
- 3. The effects of HTD1801 on liver-associated enzymes;
- 4. The effects of HTD1801 on biomarkers of liver inflammation and fibrosis;
- 5. The effects of HTD1801 on bile acid homeostasis;
- 6. The safety and tolerability of HTD1801.

3.0 STUDY DESIGN

3.1 BASIC DESIGN CHARACTERISTICS

This multicenter, randomized, double-blind, parallel-group, POC and dose-ranging study will compare multiple doses of HTD1801 to placebo. Upon confirmation of eligibility, subjects will be randomized in a 1:1:1 ratio to receive 1 of 2 doses of HTD1801 or placebo for 18 weeks.

Subjects will receive 500 mg HTD1801, 1,000 mg HTD1801, or placebo (collectively, the study drug or study drugs), administered twice daily (BID) during the 18-week Double-Blind Treatment Period. Clinic visits for efficacy assessments and safety monitoring will occur at Week 2, then every 4 weeks throughout the Double-Blind Treatment Period. A follow-up safety telephone contact for an assessment of adverse events (AEs) and concomitant medications will take place at least 30 days after the last dose of study drug. An interim analysis will be conducted after a minimum of 51 subjects complete the assessment of the primary efficacy endpoint to assess sample size assumptions and futility through conditional power; the study will not be stopped for efficacy. An independent Data and Safety Monitoring Board (DSMB) will provide additional safety oversight.

3.2 DURATION OF SUBJECT PARTICIPATION AND STUDY

Once the informed consent form (ICF) is signed, Screening assessments (see Section 5.1.1) may be performed over a 28-day period prior to randomization at the Baseline visit. Subjects will then be randomized to receive their assigned study drug during the 18-week Double-Blind Treatment Period (see Section 5.1.3). If a subject completes the Double-Blind Treatment Period or discontinues his/her assigned study drug early, the subject will complete follow-up assessments (see Section 5.1.5) at least 30 days after the last dose of study drug. Overall subject participation, from Screening through the follow-up assessments, may last for up to approximately 6 months.

The study begins when the first subject signs the ICF. The end of the study will occur when all subjects have discontinued taking their assigned study drug (i.e., either at the end of the Double-Blind Treatment Period or earlier) and have completed the follow-up assessments.

3.3 STUDY POPULATION

Approximately 117 patients with NASH and T2DM will be enrolled as subjects from approximately 15 investigational sites in the US. Eligibility will be established by the Investigator on the basis of the inclusion and exclusion criteria.

3.3.1 Inclusion Criteria

To be considered eligible to participate in this study, a subject must meet the inclusion criteria listed below:

- 1. Male or female between 18 and 75 years of age.
- 2. Clinical diagnosis of NASH with at least stage F1 fibrosis as evident by:
 - Liver fat content ≥10% as assessed by MRI-PDFF and a corrected T1 (cT1) of ≥830 msec as assessed by multiparametric MRI.
- 3. Aspartate aminotransferase ≥20 U/L.
- 4. Clinically documented diagnosis of T2DM ≥6 months prior to randomization.
- 5. If on a T2DM medication regimen, specifically thiazolidinediones, glucagon-like peptide-1 (GLP-1) agonists, dipeptidyl peptidase-4 (DPP-4) inhibitors, or sodium-glucose cotransporter-2 (SGLT-2) inhibitors, must be maintained on a stable dose regimen for ≥90 days prior to randomization.
- 6. If on vitamin E, must be maintained on a stable dose of ≤400 IU for ≥90 days prior to randomization with no anticipated dose increases during the study.
- 7. Regimens for other permitted concomitant medications, as described in Section 4.5 of the protocol, must be stable for ≥28 days prior to randomization.
- 8. Body mass index (BMI) >25 kg/m².
- 9. Females of child-bearing potential (FOCP) and males participating in the study must either agree to use at least 2 approved barrier methods of contraception or be completely abstinent from sexual intercourse, if this is their usual and preferred lifestyle, throughout the duration of the study and for at least 90 days after the last

dose of study drug. Females who are postmenopausal must have appropriate supporting documentation with a corresponding follicle-stimulating hormone (FSH) test result to support status.

10. Ability to understand and sign a written ICF.

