- 5. If on a T2DM medication regimen, specifically thiazolidinediones, glucagon-like peptide-1 (GLP-1) agonists, dipeptidyl peptidase-4 (DPP-4) inhibitors, or sodium-glucose cotransporter-2 (SGLT-2) inhibitors, must be maintained on a stable dose regimen for ≥90 days prior to randomization.
- 6. If on vitamin E, must be maintained on a stable dose of ≤400 IU for ≥90 days prior to randomization with no anticipated dose increases during the study.
- 7. Regimens for other permitted concomitant medications, as described in Section 4.5 of the protocol, must be stable for ≥28 days prior to randomization.
- 8. Body mass index (BMI) >25 kg/m².
- 9. Females of child-bearing potential (FOCP) and males participating in the study must either agree to use at least 2 approved barrier methods of contraception or be completely abstinent from sexual intercourse, if this is their usual and preferred lifestyle, throughout the duration of the study and for at least 90 days after the last dose of study drug. Females who are postmenopausal must have appropriate supporting documentation with a corresponding follicle-stimulating hormone (FSH) test result to support status.
- 10. Ability to understand and sign a written informed consent form (ICF).

Exclusion criteria:

- 1. Clinically significant acute or chronic liver disease unrelated to NASH, including but not limited to primary sclerosing cholangitis (PSC), Wilson's disease, alpha-1 antitrypsin (AAT) deficiency (MZ or ZZ phenotype), hepatitis B or C, hereditary hemochromatosis, alcoholic liver disease, and drug-induced liver disease.
- 2. Clinically or histologically documented cirrhosis.
- 3. Poorly controlled T2DM (HbA1c ≥9.5%) or Type 1 Diabetes Mellitus.
- 4. Hepatitis B surface antigen positive.
- 5. Hepatitis C antibody positive with active infection.
- 6. Human immunodeficiency virus (HIV)-1 or HIV-2 infection.
- 7. Glucose-6-phosphate dehydrogenase (G6PD) deficiency.
- 8. Any prior history of hepatic decompensation (encephalopathy, ascites, gastroesophageal varices, hepatorenal syndrome), platelet count <150,000/mm³, international normalized ratio (INR) ≥1.3 despite vitamin K supplementation, serum albumin <3.2 g/dL, or a prior or planned liver transplantation.
- 9. History of alcohol or substance abuse or dependence.
- 10. Hepatic steatosis that, in the opinion of the Investigator, is primarily related to alcohol consumption.
- 11. Inability to undergo MRI for any reason.

STUDY SYNOPSIS (continued)

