An absolute change in LFC of 5% as measured by MRI-PDFF has been reported to be the minimal clinically relevant difference between active treatment and placebo that correlates with histological improvement in NASH (Loomba et al., 2015, Patel et al., 2015). Furthermore, Harrison and colleagues reported a pooled standard deviation of 6.3% for changes from Baseline in LFC (Harrison et al., 2018). Based on this standard deviation, 35 subjects in each treatment group will provide 90% power to show a difference of 5 percentage points between any 2 treatment groups at the 5% level of significance. To allow for a dropout rate of 10%, 39 subjects will be randomized to each of the 3 treatment groups. An interim analysis will be conducted after a minimum of 51 subjects complete the assessment of the primary efficacy endpoint to assess sample size assumptions and futility through conditional power; the study will not be stopped for efficacy.

Figure 1. Study Design

| Screening | Baseline | WK 2 | WK 6 | WK 10 | WK 14 | WK 18 | Follow-up |
|-----------|----------|------|------|-------|-------|-------|-----------|

[figure not shown]

 Table 1.
 Schedule of Time and Events

| | Protocol | | | | Double-Blin | nd Treatment | | | | |
|--|--------------|-----------|----------|------|-------------|--------------|-------|-------|----|-----------|
| | Section(s) | SCR | Baseline | WK 2 | WK 6 | WK 10 | WK 14 | WK 18 | ET | Follow-up |
| Visit Day | | -28 to -1 | 0 | 14 | 42 | 70 | 98 | 126 | | +30d |
| Procedure / Window | _ | - | - | ±3d | ±3d | ±3d | ±3d | ±3d | - | +7d |
| Administrative Procedures | | | | | • |   | • | | | • |
| Clinic visit | 5.1 | X | X | X | X | X | X | X | X | |
| Informed consent | 10.1 | X | | | | | | | | |
| Eligibility criteria | 3.3.1, 3.3.2 | X | Xa | | | | | | | |
| Demographics | 6.1.1 | X | | | | | | | | |
| Medical history | 6.1.1 | X | Xa | | | | | | | |
| Randomization | 6.1.2 | | X | | | | | | | |
| Dispense study drug | 6.1.2 | | X | X | X | X | X | | | |
| Return study drug | 6.1.2 | | | X | X | X | X | X | X | |
| Study discharge | 5.1.4, 5.1.5 | | | | | | | X | X | |
| Telephone contact | 5.1.6 | | | | | | | | | X |
| Clinical Assessments | | | | | | | | | | |
| Comprehensive physical examination | 6.3.1 | X | | | | | | X | X | |
| Targeted physical examination ^b | 6.3.1 | | Xa | | X | | X | | | |
| Vital signs | 6.3.2 | X | Xa | | X | | X | X | X | |
| Weight | 6.3.2 | X | Xa | X | X | X | X | X | X | |

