5.1.4 Study Discharge

Following the successful completion of all procedures at the Week 18 visit of the Double-Blind Treatment Period, all subjects are to undergo study discharge procedures. This will include instructions to the subject to contact the investigational site immediately if any problems or concerns arise during the next 30 days of follow-up (see Section 5.1.6).

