5.1.5 Early Termination

Should a subject permanently discontinue taking his/her assigned study drug, an Early Termination (ET) visit should be performed. The ET visit procedures and assessments are the same as those performed at the Week 18 visit (see Section 5.1.3). If the ET visit coincides with a regularly scheduled study visit, the ET visit procedures and assessments will be performed in its place. The subject will then be instructed to contact the investigational site immediately if any problems or concerns arise during the next 30 days of follow-up (see Section 5.1.6).

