5.1.6 Follow-up Period

All subjects will undergo follow-up evaluations at least 30 days after the last dose of study drug. The follow-up can be via telephone, provided that the subject has no health concerns related to the study. The subject may be asked to return to the investigational site if the Investigator thinks it is advisable for safety reasons. The following assessments will be conducted by telephone (or other) contact:

- AE monitoring
- Concomitant medications (query for any possible relationship to an AE)

Following the completion of the follow-up procedures, the subject is officially discharged from the study.

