7.10 PREGNANCY

When any member of the investigational site staff becomes aware of a subject's (or subject's partner's) pregnancy, the site staff must report the pregnancy to the Sponsor's or designee's pharmacovigilance department within 24 hours by using the Pregnancy Notification Form. The female subject will discontinue study drug. The pregnancy will be followed until there is an outcome and the outcome is reported to the Sponsor. Pregnancy is not to be reported as an AE.

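### Contraception is required for at least 90 days after the last dose, but planned contact ends at about day 30 to 37, so pregnancies in the rest of that period are not actively ascertained and may be missed

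*Protocol*

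**What the plan says.** - **Contraception.** Protocol 3.3.1, criterion 9, repeated in the synopsis, applies to females of child-bearing potential and to males. The commitment runs "throughout the duration of the study and for at least 90 days after the last" dose.
- **Instruction at the end of treatment.** Under 5.1.4, completers are told to "contact the investigational site immediately if any problems or concerns arise during the next 30 days of follow-up". Section 5.1.5 gives the same instruction after early termination: "if any problems or concerns arise during the next 30 days of follow-up".
- **Final contact.** Section 5.1.6 states: "All subjects will undergo follow-up evaluations at least 30 days after the last dose of study drug". Table 1 places this contact at +30 days with a +7 day window. It may be by telephone and lists two items, adverse events and concomitant medications. Then: "Following the completion of the follow-up procedures, the subject is officially discharged from the study".
- **Pregnancy tests.** In Table 1 the last scheduled test is at Week 18 or early termination, for females of child-bearing potential.
- **Pregnancy reporting.** Section 7.10 requires a report within 24 hours once any site staff member learns that a subject or a subject's partner is pregnant. It adds: "The pregnancy will be followed until there is an outcome and the outcome is reported to the Sponsor". It sets no end date and says that pregnancy is not an adverse event.

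**The concern.** The contraception requirement and the planned contact after the last dose cover different lengths of time. Section 7.10 commits the sponsor to follow known pregnancies to outcome, and 7.2 makes a congenital anomaly or birth defect in a subject's offspring a serious adverse event. Both depend on the site learning of the pregnancy. After the follow-up call, nothing in the protocol body prompts a subject to tell the site. Partners of male subjects are never tested or contacted, so a partner's pregnancy reaches the site only if the subject volunteers it.

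What is at stake is the completeness of the safety record on pregnancies after treatment. No efficacy endpoint, sample size or error rate is involved.

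**Working it through.** **Inputs**
- Screening: up to 28 days (3.2, Table 1).
- Week 18 visit: day 126, window ±3 days (Table 1).
- Follow-up contact: +30 days, window +7 days (Table 1).
- Contraception after the last dose: at least 90 days (3.3.1, criterion 9).

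**Step 1. Reproduce the plan's own duration.** Section 3.2 gives participation, from Screening through the follow-up assessments, as up to about 6 months.
- Without windows: 28 + 126 + 30 = 184 days; 184 / (365.25 / 12) = 6.05 months.
- With the late windows: 28 + 126 + 3 + 37 = 194 days, or 6.37 months.

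The stated figure therefore matches a follow-up that ends at about day 30 to 37. A last contact at day 90 would give 28 + 126 + 90 = 244 days, or 8.0 months, so no contact that late is built into the plan.

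**Step 2. Part of the contraception period after the last planned contact.**
- Contact at day 30: 90 − 30 = 60 days; 60 / 90 = 67%.
- Contact at day 37: 90 − 37 = 53 days; 53 / 90 = 59%.

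Because 90 days is a minimum, these are minimum lengths for a contact made within the Table 1 window. Section 5.1.6 sets 30 days as a minimum too; the upper limit of 37 comes from Table 1 alone.

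**Step 3. Follow a pregnancy through the text.** Suppose a subject or partner is found to be pregnant on day 60 after the last dose.
- The scheduled tests are over, and a partner never had one.
- The follow-up call has taken place and the subject has been discharged.
- The 30-day period named in 5.1.4 and 5.1.5 has passed.
- If the site nevertheless hears of it, 7.10 applies in full: report within 24 hours and follow to outcome.
- If the site does not hear of it, no step in the protocol body would bring it to light.

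**Step 4. The call itself.** It lists adverse events and concomitant medications, and 7.10 keeps pregnancy out of the adverse events. A subject may mention a pregnancy, but no item asks about one. Counting the gap from the call is thus the lenient choice.

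The documents give no pregnancy rate and no split of the roughly 117 subjects by sex or child-bearing potential, so the expected number of missed pregnancies cannot be calculated.

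**The case against.** A reader might infer that pregnancies after the call go unreported, or that reporting stops at 30 days. The documents do not support this. Section 7.10 has no cut-off, and a pregnancy that the site learns of on day 60 must be reported. Sections 5.1.4 and 5.1.5 give a 30-day instruction, but they do not say it is the sole instruction and do not discourage later contact. What is missing is active ascertainment; the duty to report remains.

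It can also be said that there is no contradiction. A contraception commitment and a safety-contact period are different provisions, and a site can comply with both. That stands: this is a gap between provisions, not a conflict. The documents give no reason for the 90 days and no elimination figure, so it cannot be claimed that a conception late in that period is an exposed pregnancy.

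The strongest point is that an instruction to report pregnancy would naturally sit in the consent form, which was not available for review. Appendix A requires the form to cover the subject's responsibilities, foreseeable risks to an embryo or fetus, and whom to contact. Such wording may therefore exist. Two facts limit this reply. Appendix A's list does not name pregnancy reporting, and 10.1 has the investigator or site prepare the form, subject to sponsor approval. Uniform wording across about 15 sites would need to come from the protocol.

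Finally, the numbers are probably small. Criterion 9 requires two barrier methods or abstinence, and no analysis or stopping rule uses pregnancies from this period. That also stands, and it is why the priority is low.

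**Conclusion.** The point holds as a gap in ascertainment. Judged on the protocol body, at least 53 to 60 of the 90 days (59 to 67%) carry a contraception requirement with no planned contact, test or reporting prompt. Subject and partner pregnancies first recognised in those days may be missed, because 7.10 acts only on what the site happens to learn.

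This rests on two assumptions: the follow-up contact falls within the Table 1 window, and no unseen document, such as the consent form or the Study Procedures Manual, already carries the instruction. The number of pregnancies affected is unknown and probably small. Low priority, with no effect on the efficacy analysis.

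**What to change.** Reconcile 3.3.1, 5.1.4, 5.1.5, 5.1.6 and 7.10. The discharge and early termination instruction and the pregnancy-reporting text should cover subject and partner pregnancies for the same period in which the protocol requires contraception. The consent wording should match.

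This concerns a reporting instruction only. It takes no position on how long contraception should last and proposes no contraceptive rule, visit or test. Since no contact is added, the participation figure in 3.2 can stand.

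The cost is about one sentence in each place and a small reporting burden after discharge. Sites would need to keep a route open for such reports after the last follow-up call, which is when 3.2 ends the study, and any pregnancy reported would be followed to outcome as 7.10 already requires.
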